APPENDIX 1:

1. Informed Consent form for the patient - Versie 1.2
2. Informed Consent form for the legal representative of the patient - Versie 1.2
3. Opting out form for the patient - Versie 1.2
4. Informed Consent form for the healthy volunteer - Versie 1.2

1. Study Synopsis

Title of clinical study	The Dynamics of the ACTH and cortisol response to CRH stimulation during critical illness: A Randomized, double-blind, placebo-controlled crossover study
Protocol Short Title/Acronym	DACAR
Sponsor name	UZ Leuven
Principal Investigator	[name]. [name]
Medical condition or disease under investigation	Critically ill patients
Purpose of clinical study	To elucidate the central cause of the low circulating ACTH concentrations in the face of elevated circulating cortisol during acute, intermediate and prolonged critical illness
Primary objective	To document the ACTH and cortisol responses to exogenous CRH in patients with acute and prolonged critical illness
Secondary objective(s)	To describe the clinical causes/consequences of these changes
Study Design	Randomized, double-blind, placebo-controlled crossover study
Primary endpoints	The responses of plasma ACTH and cortisol to CRH and the changes hereof over time in ICU in relation to patient characteristics and outcome parameters
Sample Size	At least 120 patients - patient recruitment will continue until preset sample numbers are reached in 3 time-in-ICU-cohorts (40 patients per cohort) with a comparable distribution of ICU admission categories – and 20 healthy volunteers (controls who never stayed in the ICU)
Summary of eligibility criteria	Critically ill patients in the acute phase (ICU day 3-6), the intermediate phase (ICU day 7-16) and prolonged phase (ICU day 17-28) of critical illness
Maximum duration of treatment of a Subject	Not applicable
Version and date of final protocol	1.3; 05-07-2016
Version and date of protocol amendments	-

2. Background and rationale

Cortisol, ACTH, and CRH are essential components of the 'fight and flight' response to the stress of illness and trauma. When the brain of a healthy subject senses a stressful event, the hypothalamic-pituitary-adrenal (HPA) axis is activated, releasing the hypothalamic corticotropin-releasing hormone (CRH) that stimulates the corticotrophs of the anterior pituitary gland to secrete adrenocorticotropic hormone (ACTH) which drives cortisol synthesis and secretion from the adrenal cortex. Cortisol exerts feedback inhibition at the pituitary and the hypothalamic level, hence controlling its own release.

In patients suffering from critical illness, an extreme example of physical stress, the increased availability of cortisol does not seem to originate from this typical pattern of an entirely activated HPA axis. We recently demonstrated that plasma ACTH concentrations are in fact lower than in healthy subjects, while plasma cortisol concentrations remain elevated from the first day in ICU throughout at least the first week of critical illness.¹ This is known as the 'ACTH-cortisol dissociation' during critical illness. Furthermore, we showed that these elevated plasma cortisol concentrations are only to a limited extent explained by increased cortisol production. Instead, increased cortisol availability during critical illness is largely brought about via suppressed cortisol breakdown.¹ Consequently, maintaining these high circulating cortisol levels via reduced cortisol metabolism could potentially exert negative feedback inhibition on the central components of the HPA axis, as such explaining the low plasma ACTH concentrations. This would be similar to the inhibition of both ACTH synthesis and secretion from the pituitary corticotrophs and suppressed hypothalamic CRH synthesis and secretion in response to a prolonged exposure (24h or more) to high doses of exogenous corticosteroids.²

However, the hypothalamic-pituitary feedback regulation appears much more complex than the initially proposed simple closed loop feedback system.³ For example, whereas TSH becomes completely unresponsive to TRH when thyroid hormone levels are high⁴, CRH can break through the feedback inhibition exerted by high cortisol levels.^{5,6} Furthermore, many afferent inputs from different suprahypothalamic brain regions, also targeted by cortisol, can influence CRH neuronal function in the hypothalamus, thereby regulating the set-point of pituitary responsiveness to cortisol.³ An important regulator is the hippocampus, which is capable of inhibiting stress-induced activation of the HPA axis response, and which in turn is activated by cortisol.⁷ Given the fact that prolonged elevation of cortisol evokes a reduction in hippocampal neurons and glucocorticoid receptors, this may cause a loss of feedback sensitivity of the HPA axis during chronic stress.

Our recent insights reshaped the understanding of HPA axis regulation during critical illness. In a mixed ICU population we documented that hypercortisolemia, during the first week of critical illness, coincided with suppressed nocturnal pulsatile ACTH and cortisol secretion rates, whereas the cortisol response to endogenous ACTH was overall unaltered.⁸ Therefore, these findings argue against the dogma of an activated HPA axis, and could in fact be explained by a suppression of the central components of the HPA axis in response to critical illness. However, it remains unknown

whether and to what extent the elevated plasma cortisol concentrations in ICU patients evoke feedback-inhibition at the level of the hypothalamus and/or the pituitary, and whether and how this suppressive effect evolves with the duration of critical illness. One could speculate that the longer the feedback-inhibition persists, the more CRH and/or ACTH synthesis and secretion would be suppressed. However, the progressive loss of responsiveness of the HPA axis to negative feedback regulation, due to the degenerative changes in the hippocampus, could also play a role.⁷ On the other hand, long-term administration of exogenous glucocorticoids or endogenously elevated plasma cortisol concentrations in patients with Cushing syndrome have been shown to cause tertiary, and not secondary, adrenal insufficiency by prolonged suppression of the hypothalamic CRH neurons and/or its higher regulatory inputs.⁹

Given the important function of ACTH in ensuring adrenal functional and structural integrity, a sustained central CRH and/or ACTH deprivation could explain the increased incidence of absolute adrenal insufficiency in the prolonged phase of critical illness.¹⁰ The CRH stimulation test has been used to diagnose adrenal insufficiency and to differentiate between primary or secondary causes, by measuring the ACTH and cortisol response to intravenous CRH injection.¹¹ Currently, the test is commonly used but only few studies were done in critically ill patients.¹²⁻¹⁵ Unfortunately, large enough and well-designed prospective clinical studies of CRH stimulation tests performed in critical ill patients at different time points during the course of their illness are currently lacking. As such, documenting a change in ACTH and/or cortisol response to CRH over time could be highly informative to understand illness evolution and might open perspectives for new therapeutic strategies.

3. Study objectives and Design

3.1 Study objectives

Our *primary objective* is to compare the ACTH and cortisol responses to exogenous CRH in patients with increasing duration of critical illness. Therefore we will investigate 3 cohorts of critically ill patients, matched for baseline characteristics (equal proportions of primary diagnostic category on ICU admission), during the acute, the intermediate and the prolonged phase of critical illness and compare these with a matched healthy control group. Cortisol binding proteins will also be assessed to calculate free cortisol. This will allow us to gain further insights in the potential (loss of) suppression of the central HPA axis in response to critical illness as well as any eventual evolution to (absolute) adrenal failure. To further reduce the impact of confounding covariates, each patient will serve as his or her own control in a crossover design. Our *secondary objective* is to describe the possible causes/consequences of such changes within the HPA-axis.

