4.3. Expected duration of the study

a. Time window of monitoring per patient:

Patients from each cohort will be studied during a total period of 4.5 hours, with repetitive blood sampling during 2 consecutive mornings from 10.45-13.00 h, after receiving an alternate injection of CRH or placebo each morning. To use the crossover design, the effects of the intervention during the first period (i.e. effect of CRH) must not carry over into the second period.¹⁶ Firstly, taking the half-life of hCRH (30.5 +/- 3.3 min) into account, the requirement for a wash-out of 5 times the drug half-life (152.5 min) is sufficient to meet this assumption.¹⁷ Secondly, based on the fact that the cortisol clearance is reduced with at least 50% in critical ill patients than in healthy individuals, it is justifiable to perform the second alternate injection on the morning after the first injection.¹

b. Calculated sample size:

Based on the available literature⁹, we calculated to require 20 patients per cohort in order to detect a potential Cushing-like suppression of the ACTH response to CRH in critically ill patients, in comparison with the response of 20 healthy volunteers, with an alpha error of 1% (to correct for the multiple comparisons of each of the 3 patient cohorts with the healthy controls) and >80% power. In more detail: we expect an effect size of 1.20 based on previous findings, reporting a difference of mean delta AUC ACTH of 2159 to 795 pmol L⁻¹ min, with a common standard deviation of 1136 pmol L⁻¹ min.⁹ Power calculation was performed with an independent T-test for comparison of 2 means, assuming equal variances.

To take into account a potential increase in variation due to the heterogenous critical illnesses, we will double the number of patients to 40 per cohort. With 40 patients per cohort, we can detect a reduction of 30% in the ACTH responses to CRH between 2 patient cohorts, with an alpha error of 5% and >80% power (power calculation was performed as explained above, based on a reduction of 30% of 2159 pmol L⁻¹ min with the same standard deviation⁹). Recruitment of patients will continue until the preset number of 40 patients is reached in the 3 patient cohorts, with equal proportions of ICU admission categories among the groups.

c. Study duration:

Based on a retrospective analysis of the mean stay of patients in the ICU, we estimate that the study will take approximately one year to finalize recruitment.

5. Study Procedures and sample collection

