5.2 Control group

Time profiles of ACTH and cortisol response to exogenous CRH are not clearly defined in the literature. Especially data from healthy volunteers with a comparable age, gender and BMI as our patient population are lacking. To compare the evolution of the ACTH and cortisol response during critical illness with healthy reference values, we will use the same study protocol as for the patients in 20 demographically matched healthy volunteers, with repetitive blood sampling during 2 consecutive mornings from 10.45-13.00 h, after receiving an alternate injection of CRH or placebo each morning. Volunteers will be asked to limit their morning nutritional intake to a European breakfast.

6. Compensation for control group

Healthy control subjects will be compensated for all expenses made to participate in the study, such as transportation cost and costs for parking space, and will be offered a meal on each study day and an overnight stay in Leuven. Furthermore, a gift card (value card worth 50 EUR) will be offered as an additional reward.

7. Statistics

First, the response to CRH injection (changes over time in plasma ACTH and cortisol concentrations) will be corrected for its corresponding placebo test result (changes over time in plasma ACTH and cortisol concentrations), resulting in a delta AUC value. The delta AUC values will be compared between each of the 3 cohorts and the healthy reference group, with correction for multiple comparisons with use of ANOVA (Bonferroni correction of the alpha error to correct for the multiple comparisons of each of the 3 patient cohorts with the healthy controls), after transforming the data to normally distributed values if needed. If the latter is not possible, non-parametrical tests will be used.

Second, for those patients from whom multiple CRH test results were collected, changes in delta AUC values within these patients will be analyzed with use of mixed models / repeated measures ANOVA after transforming the data to normally distributed values if needed.

Third, correlations between the ACTH and cortisol responses to exogenous CRH and clinical risk and outcome parameters will be done with the use of Pearson tests. Fourth, these measurements will be compared in patients with a favorable and a non-favorable clinical outcome.

8. Ethics and regulatory approvals

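### The primary objective is change in CRH response with duration of critical illness, but section 7 tests each cohort only against healthy controls, so change would be read from which cohorts reach significance

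*Protocol*

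**What the plan says.** The synopsis gives the purpose as "To elucidate the central cause of the low circulating ACTH concentrations in the face of elevated circulating cortisol", across the acute, intermediate and prolonged phases. The Background (section 2) calls it unknown whether raised cortisol levels "evoke feedback-inhibition at the level of the hypothalamus and/or the pituitary, and whether and how this suppressive effect evolves with the duration of critical illness". Section 3.1 makes comparison of patients with increasing duration of illness the primary objective, adds a comparison with matched healthy controls, and says: "This will allow us to gain further insights in the potential (loss of) suppression of the central HPA axis in response to critical illness".

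Section 4.3 b sizes two different comparisons:
- Cohort against controls: 20 per group at alpha 1%, "in order to detect a potential Cushing-like suppression of the ACTH response to CRH in critically ill patients, in comparison with the response of 20" controls.
- Cohort against cohort: after doubling to 40 patients per cohort, "we can detect a reduction of 30% in the ACTH responses to CRH between 2 patient cohorts", at alpha 5% with more than 80% power.

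Section 7 carries only the first of these into the primary analysis: "The delta AUC values will be compared between each of the 3 cohorts and the healthy reference group, with correction for multiple comparisons with use" (the method named is ANOVA), with Bonferroni correction for the three cohort-against-control comparisons. Its second step analyses change within patients who were tested more than once, but section 4.1 keeps those repeat tests out of the primary study. Section 7 names no contrast between the three independent cohorts.

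**The concern.** The question of change with duration of illness is a question about differences between cohorts. If the only primary tests are against controls, the natural way to answer it is to see which cohorts are significant. A difference between significant and non-significant is not itself a tested difference: two cohorts with the same true response can fall on opposite sides of the threshold by chance.

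The risk is larger here because the control comparison was planned for a very large effect and uses a strict alpha. A moderate suppression will often be non-significant. A paper could then describe suppression as appearing, persisting or being lost when the responses were the same, or describe a cohort as normal when the data do not show that.

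**Working it through.** **Inputs (section 4.3 b).** Control mean 2159, suppressed mean 795, common SD 1136 (pmol/L min), 40 patients per cohort, 20 controls, equal-variance t-test. Alpha against controls is 1% in 4.3 b. Section 7 says Bonferroni over three comparisons, taken as 0.05/3 = 1.67% (the overall 5% is an assumption). Tests are taken as two-sided; the protocol does not say.

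**1. The plan's own figures.**
- Difference 2159 − 795 = 1364, which is 1364/2159 = 63% and 1364/1136 = 1.20 SD. For 20 against 20 at 1%, noncentral-t power is 85%, so the stated figure of more than 80% holds.
- A 30% reduction is 0.30 × 2159 = 648, or 648/1136 = 0.57 SD. For 40 against 40 at 5%, power is 71% two-sided and 81% one-sided, so that claim reproduces only one-sided.

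**2. Cohort against controls, 40 against 20.** SE = 1136 × √(1/40 + 1/20) = 311, df = 58. Miss rate = 1 − noncentral-t power:

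| True reduction | In SD units | Missed at 1% | Missed at 1.67% |
|---|---|---|---|
| 30% (648) | 0.57 | 71% | 64% |
| 40% (864) | 0.76 | 45% | 38% |
| 50% (1080) | 0.95 | 21% | 16% |
| 63% (1364) | 1.20 | 5% | 3% |

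Using the error term pooled over all four groups (df = 136), the 30% row becomes 70% and 63%. The reduction with 80% power is 1095/2159 = 51% at 1% and 1032/2159 = 48% at 1.67%.

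**3. What a null result would exclude.** With an observed difference of exactly zero, the 98.3% interval is ±2.465 × 311 = ±767, and 767/2159 = 36%. A 30% suppression would still be inside it.

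**4. Same suppression in all three cohorts.** I simulated 200,000 trials with normal data, SD 1136, three cohorts of 40 with the same true mean and 20 shared controls. Percentage of trials with one or two cohorts significant but not all three:

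| True reduction in every cohort | Pooled ANOVA error, 1% / 1.67% | Separate t-tests, 1% / 1.67% |
|---|---|---|
| 30% | 34% / 37% | 35% / 38% |
| 40% | 39% / 37% | 41% / 39% |

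With the pooled error, no cohort is significant in 52% / 44% of trials at 30% and 24% / 18% at 40%.

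**5. The direct contrast.** For 40 against 40, SE = 1136 × √(1/40 + 1/40) = 254. The 95% half-width is 1.991 × 254 = 506, or 506/2159 = 23% of the control mean. It is more precise than either control comparison, and the patients are already planned.

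**The case against.** The strongest reply is that the misreading is not in the protocol. Nowhere does it say that a non-significant comparison with controls will count as a preserved response, a hypothalamic cause or a loss of suppression; section 3.1 promises only insights. That stands, and it limits the point to a risk in interpretation.

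A reader might go further and infer that the trial plans to place the cause at the hypothalamus whenever a cohort does not differ from controls. The hypothalamus-or-pituitary question makes this tempting, as does the remark that glucocorticoid excess and Cushing syndrome "have been shown to cause tertiary, and not secondary, adrenal insufficiency". The documents do not support it. The Background also says CRH can overcome feedback inhibition by high cortisol, so a normal response would not by itself clear the pituitary. The source cited for the tertiary pattern also supplies the reduced response used for sample size. No mapping from result to level is fixed.

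It is also fair to say that 30% is a target only between patient cohorts. Against controls the stated target is 63%, and that is well powered. The 30% miss rate therefore shows what a non-significant result can mean; it is not a failed design target. On a one-sided reading the 30% miss rate is 53-62%, though ANOVA contrasts are normally two-sided.

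Loss of suppression can indeed be shown by a positive difference, namely a larger response in later cohorts. That argues for the between-cohort contrast, which section 7 does not name. A statistical analysis plan might add it, but section 7 does set out the primary comparisons and their correction, and these do not match section 3.1 or the second calculation in 4.3 b.

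**Conclusion.** The point holds as a mismatch between objective and primary analysis. Section 3.1 asks about change with duration of illness, 4.3 b sizes a between-cohort comparison, and section 7 tests only against controls. Reading change from the pattern of significance would give mixed verdicts in about 34-39% of trials (pooled error; up to 41% with separate t-tests) when all cohorts share the same 30-40% suppression. The control comparison has 80% power only for reductions of about 48-51% or more.

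These figures rest on the protocol's mean and SD, two-sided tests, normal data and equal variances. If the SD were 1.25 times larger in both groups (an assumed value, prompted by the protocol's own worry about heterogeneous patients), the 30% miss rate would be 78-83%. The difference test remains valid for its planned effect. The documents do not support a charge that the protocol equates non-significance with a normal response.

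**What to change.** In section 7:
- Add direct between-cohort contrasts of delta AUC, with confidence intervals and a stated alpha and sidedness, as the analysis of change with duration of illness.
- Give each cohort-against-control difference with its confidence interval.
- State that neither a non-significant control comparison, nor one cohort being significant and another not, will be taken as evidence of a preserved response or of loss of suppression.

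In section 4.3 b, state that 40 against 20 has 80% power only for reductions of about 48-51% or more.

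No equivalence margin is proposed. A 50% margin is tempting because the planned numbers could meet it: 93% probability if the true difference is zero, one-sided 2.5%. But the documents give no basis for it, and a true 30% suppression would be called preserved in about 28% of trials (noncentral t, 0.20 × 2159/311 = 1.39, df 58). If the sponsor wants to claim a preserved response, it should justify a margin before the data are seen.

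The cost is a few sentences, with no extra patients or samples. Some cohorts will be reported as inconclusive. The added contrasts need an alpha: for a 30% difference between cohorts of 40, two-sided power is 71% at 5% and 54% if 5% is split over three contrasts.

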3.2 Study Design

A randomized, double-blind, placebo-controlled crossover study

4. Selection of subjects

4.1 Patients

We will study unique patients from different time cohorts, with an increasing duration of critical illness, in order to have 3 sets of patients who represent 3 different time points in the course of critical illness:

Cohort 1: acute phase of critical illness: ICU day 3 to 6.

Cohort 2: intermediate phase of critical illness: ICU day 7 to 16.

Cohort 3: prolonged phase of critical illness: ICU day 17 to 28.

If a patient, who was included in an earlier cohort, is still in ICU at the time point of the next cohort recruitment, and still meets the inclusion criteria, the patient will be studied again according to the same study protocol. The results from these analyses within patients over time will not be included in the primary study to avoid bias due to multiple comparisons, but will be analyzed separately. The availability of such sequential responses over time within one patient will allow an additional longitudinal analysis of HPA-axis alterations during the time course of the disease.

Two times each week, all adult (age ≥ 18 y) patients from the population present in 5 ICUs from 2 departments (medical and surgical) in the University Hospital of Leuven will be screened for eligibility in the study. Patients will be included when written informed consent by the patient or patients' next of kin is given.

Inclusion criteria

All adult (age ≥ 18 y) patients at the surgical or medical intensive care units, with ongoing intensive care dependency, a stable condition for at least 48h, and an expected stay in ICU for at least 48h, are eligible.

Exclusion criteria

- Predisposing factors of adrenal insufficiency
 - Cerebral disease with intracranial hypertension threatening the neuroendocrine system
 - Pituitary disorders including (pan)hypopituitarism
 - Known adrenal disease (Cushing's syndrome or Addison's disease)
 - Chronic treatment with glucocorticoids, other steroids or anti-steroid chemotherapy within the last 3 months
 - IV administration of glucocorticoids within the last 72 hours
 - Use of etomidate within the last 72 hours
 - Use of azoles within the last 7 days

- Other drugs predisposing to adrenal insufficiency: phenytoin, rifampicin, glitazones, imipramin, phenothiazine, phenobarbital
- Patients known to be pregnant or nursing
- No arterial line or central venous catheter in place
- Ethical restrictions
 - Moribund
 - Declined participation

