Patient characteristics and outcome parameters: demographics (age, gender, BMI), medical history (diabetes, malignancy, renal replacement therapy), admission characteristics (reason for ICU admission, APACHE II score, SIRS and sepsis on admission), patient characteristics during ICU stay (clinical evidence of adrenal failure, SIRS and sepsis), ICU and hospital stay, ICU and hospital mortality.

Clinical parameters: Among others vital parameters (mean, systolic and diastolic blood pressure, pulse, temperature), mechanical ventilation, mean daily glycemia and renal function (daily urinary volume, creatinine clearance), infection.

Treatment information: all relevant treatments such as vasopressors and inotropes, treatment with opioids, anti-coagulants, insulin, and types and amounts of nutrients.

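### A difference between the three time-in-ICU cohorts mixes change with illness duration and change in who is still in the ICU, so it cannot on its own be read as change over time

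*Protocol*

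**What the plan says.** Protocol section 4.1 defines three windows: "Cohort 1: acute phase of critical illness: ICU day 3 to 6", "Cohort 2: intermediate phase of critical illness: ICU day 7 to 16" and "Cohort 3: prolonged phase of critical illness: ICU day 17 to 28". The primary study uses different patients in each, "in order to have 3 sets of patients who represent 3 different time points in the course of critical illness". The same eligibility rules apply to all three: still dependent on intensive care, stable for 48 h, expected to stay at least 48 h more, an arterial line or central venous catheter in place, and not moribund.

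The reading across duration appears in three further places. The synopsis gives the primary endpoint as "The responses of plasma ACTH and cortisol to CRH and the changes hereof over time in ICU". Section 3.1 makes comparison across increasing duration of illness the primary objective and hopes to learn about a possible evolution to adrenal failure. Section 4.3b states that with 40 per cohort "we can detect a reduction of 30% in the ACTH responses to CRH between 2 patient cohorts".

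The only balancing between cohorts is on diagnostic category at ICU admission (3.1, 4.3b). In section 7, "The delta AUC values will be compared between each of the 3 cohorts and the healthy reference group", with Bonferroni correction. Patients still in the ICU at the next window are retested. Those results are kept out of the primary study (4.1) and analysed by mixed models or repeated measures ANOVA (7). Section 7 also plans to relate the responses to outcome, and section 5.1 records "ICU and hospital stay, ICU and hospital mortality".

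**The concern.** A patient can enter cohort 3 only by being alive and still in the ICU at day 17. Cohort 1 contains patients who will get that far together with patients who will die or be discharged first. If these groups already respond differently to CRH at day 3–6, cohorts 1 and 3 will differ even though no patient's response has changed.

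The stated safeguards do not reach this:

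- Balance on admission category acts before the selection takes place.
- The crossover makes each patient his or her own control for CRH against placebo, not for early against late illness.
- Section 7 treats a link between response and outcome as worth testing. Such a link is what would make leaving the ICU informative.

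At stake is the reading of the trend. A lower response in cohort 3 could be taken for progressive central suppression when low responders are simply those who stay. If low responders leave earlier, a real decline could be hidden.

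**Working it through.** **Inputs from the protocol (4.3b):** reference mean delta AUC 2159 pmol/L·min, SD 1136, 40 patients per cohort, alpha 5% between cohorts, target reduction 30%.

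**Inputs that are assumed (not in the protocol):**
- p, the share of cohort 1 who will still be in the ICU at day 17: 0.1 to 0.8.
- D, the difference in response already present at day 3–6 between those patients and the rest of cohort 1: 0.25 or 0.5 SD.

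**Step 1: the plan's own figure.** The target is 0.30 × 2159 = 648 pmol/L·min, or 648/1136 = 0.57 SD. A two-sample t-test with 40 against 40 has 81% power at one-sided 5%, which reproduces the stated power above 80%. At two-sided 5% it has 71%. Sidedness is not stated. The rejection rates below are two-sided.

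**Step 2: expected difference when no patient changes.** Let long-stayers have mean m and the others m + D. Then cohort 1 has mean p·m + (1−p)(m + D) = m + (1−p)D, and cohort 3 has mean m. So the expected cohort 1 minus cohort 3 difference is (1−p) × D.

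**Step 3: numbers.** For example, p = 0.1 and D = 0.25 SD gives 0.9 × 0.25 × 1136 = 256. Rejection rates come from the noncentral t distribution with 78 degrees of freedom.

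| D (SD) | p | Spurious difference (pmol/L·min) | Share of 648 | Rejection, nominal 5% |
|---|---|---|---|---|
| 0.25 | 0.1 | 256 | 39% | 17% |
| 0.25 | 0.3 | 199 | 31% | 12% |
| 0.25 | 0.5 | 142 | 22% | 9% |
| 0.25 | 0.8 | 57 | 9% | 5.6% |
| 0.5 | 0.1 | 511 | 79% | 51% |
| 0.5 | 0.3 | 398 | 61% | 34% |
| 0.5 | 0.5 | 284 | 44% | 20% |
| 0.5 | 0.8 | 114 | 18% | 7% |

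At D = 0.1 SD, rejection is only 5.6% to 6.8% for p = 0.5 down to 0.1.

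**Step 4: selection in the opposite direction.** If a true fall of 648 is opposed by selection with D = 0.25 SD, two-sided power falls from 71% to 33%, 42%, 50% or 63% for p = 0.1, 0.3, 0.5 or 0.8.

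**Step 5: what a comparison restricted to patients reaching day 17 can offer.** At p = 0.1, 0.3 or 0.5, about 4, 12 or 20 of the 40 cohort 1 patients remain. Two-sided 5% power for 648 against 40 in cohort 3 is then 19%, 40% or 53%.

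**The case against.** **Cohort 1 is already selected.** A reader might infer that cohort 1 takes all comers. Section 4.1 does not support that: the 48 h stability rule, the expected further 48 h of stay and the exclusion of moribund patients remove many imminent deaths and discharges. This narrows the contrast. It does not close it, because an expected 48 h stay from day 3–6 falls well short of day 17.

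**The specified tests are against healthy controls.** A reader might infer that the section 7 comparisons are invalid. They are not. Each one properly describes the patients present in that window. The weakness lies in the inference across cohorts invited by the synopsis and by sections 3.1, 4.1 and 4.3b.

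**Much is already planned.** The retests within patients are free of this change in composition over the interval in which each patient is observed, and outcome analyses are foreseen. That stands, and it makes the remedy cheap. But the protocol keeps the retests out of the primary study, states no sample size for them and gives them no role in interpreting the cohort contrast. They also cover only patients who stay and remain eligible.

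**The size is assumption.** This is correct. With p = 0.8 and D = 0.25 SD the bias is negligible. Deaths and discharges may also differ from long-stayers in opposite directions, so that D partly cancels.

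**Conclusion.** The concern holds for the inference about change with duration, and only for that. Differences between cohorts mix evolution within patients with a change in who remains, and nothing in the protocol separates the two in the primary comparison.

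The protocol gives neither p nor D, so neither the size nor the direction of the bias can be known in advance. It ranges from trivial to a large part of the 648 pmol/L·min the trial is sized to detect. It would be wrong to conclude that a cohort trend, if found, must be an artefact, or that it would be biased towards decline: the documents support neither statement. The improvement is worth making because it is cheap and bears on the central question about time.

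**What to change.** In section 7:

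- **(a)** Name the already planned within-patient mixed-model analysis of repeat tests as the key supporting analysis for any statement about change with duration.
- **(b)** Add a supportive comparison of cohort 3 with the cohort 1 and cohort 2 patients whose recorded ICU stay reached day 17. Within cohorts 1 and 2, report delta AUC separately for patients who stayed to day 17, who died earlier and who were discharged earlier.
- **(c)** Report these as estimates with confidence intervals. Describe a cohort difference as change with duration only as far as the within-patient and restricted estimates and their intervals support it. Otherwise, describe it as a difference between the patients present at each phase.

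Do not use a rule that only asks whether the restricted comparison points the same way. Both comparisons share cohort 3 and the same long-stayers. In simulations with no patient changing (p = 0.1 to 0.5, D = 0.25 or 0.5 SD), such a rule passed from 64% to over 99% of the spurious significant differences.

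In section 4.1, describe the cohorts as patients present in the ICU at each of three phases.

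**Cost:** wording and extra analyses of data already collected, with no added patients or samples. The restricted comparison is imprecise, as step 5 of the working shows. It is also not fully like-for-like, because primary cohort 3 excludes patients enrolled earlier. It is a check and not a cure.
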